11.2. Assessments

11.2.1. Efficacy

11.2.1.1. Plasma Glucose Monitoring

As long as the patient is receiving IV glucose, the GIR will be reviewed hourly, based on an hourly PG check performed by the StatStrip Xpress2 meter. The IV GIR will be reviewed, evaluated, and adjusted (if indicated) according to the IV GIR algorithm based on PG levels specified in Table 1. If IV glucose has been stopped, PG will be checked according to local practice, but at least 3 times daily.

Blood for PG check can be obtained either by finger or heel sticks or by an indwelling peripheral line. However, if using an indwelling peripheral line, the total blood volume drawn during a 28-day period should be considered according to Section 11.2.3.1.

At each visit, the investigator will ensure that SMPG data are downloaded from the patient's device. The investigator will check for patient compliance in SMPG measurements. The procedure for download of SMPG data will be described in the pharmacy manual/TMM.

Adjustments to the trial drug will be made as outlined in Section 10.2.

11.2.1.2. Continuous Glucose Monitoring

Dexcom CGMs, configured and labeled for use in the trial, will be provided. In Germany, only the Dexcom G6 CGM will be used. Enrollment in Germany will start only after Dexcom G6 CGM is available.

For other countries: the Dexcom G4 may be used until all required approvals for use of the Dexcom G6 are obtained, but no later than to the end of 2020, when the Dexcom G4 will be taken off the market by the supplier. Patients enrolled thereafter will all be using the Dexcom G6 CGM. Patients who started in the trial using the Dexcom G4 CGM should continue using this device throughout the trial and should not switch to the Dexcom G6 device.

The CGM will be started at least 24 hours prior to randomization and will be used during Parts 1 and 2 in a blinded mode to evaluate efficacy in terms of hypoglycemic episodes. Short pauses of 1 to 3 days due to skin irritation or discomfort are allowed during Part 2 of the trial after consultation with the investigator.

The CGM device should be calibrated and used according to the manufacturer's instructions.

At each visit, the investigator will ensure that CGM data are downloaded from the patient's device. The procedure for download of CGM data will be described in the pharmacy manual/TMM.

The contract research organization (CRO) or delegate will handle the device sourcing, configuration for use in this trial, procedures for blinded data extraction, device service, and handling of potential returns.

11.2.1.3. Diary

For patients who are discharged during the trial, the parent(s)/guardian will receive a paper diary to be completed at home. The investigator will instruct the patient's parent(s)/guardian on how to complete the diary. The following information should be recorded in the diary:

- Type and volume of fluid administered through NG tube/gastrostomy
- Hypoglycemic events, including related SMPG measurements
- Concomitant medications
- AEs
- Hospitalizations, visits to health care providers or emergency room (ER)/accident & emergency (A&E) department, and visits by paramedics
- Data regarding suspicion of NME and neurological findings

Diary entries should be reviewed at each visit and the review documented in the diary. Data from the diary entries should be transcribed to the eCRF on an ongoing basis.

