7.2.3. Secondary Efficacy Endpoints

Part 1 (Day 1 to 4, for each 48-hour treatment period)

- Mean IV GIR for each 48-hour treatment period during Part 1 (dasiglucagon or placebo administration)
- Mean IV GIR below 10 mg/kg/min in the last 12 hours of each treatment period during Part 1 (yes/no) (dasiglucagon or placebo administration)

Part 2 (Day 5 to 25, assessed from the start of treatment in part 2)

- Time to complete weaning off IV GIR.
- Hypoglycemia event rate, defined as number of hypoglycemic events (PG <70 mg/dL or 3.9 mmol/L), as detected by SMPG.
- Clinically significant hypoglycemia event rate, defined as number of events <54 mg/dL (3.0 mmol/L), as detected by SMPG.
- Time to actual hospital discharge.
- Time to pancreatic surgery (sub-total or total pancreatectomy).
- Total amount (g) of carbohydrates administered (regardless of the route) per day, together with amounts (g) of carbohydrates administered per day:
 - via IV glucose infusion, or bolus (not as part of total parenteral nutrition),
 - as part of total parenteral nutrition (if applicable),

- via oral route, and
- via NG tube or gastrostomy.
- CGM percent time in range 70-180 mg/dL (3.9-10.0 mmol/L).
- CGM percent time in hypoglycemia (<70 mg/dL or 3.9 mmol/L).
- CGM percent time in clinically significant hypoglycemia (<54 mg/dL or 3.0 mmol/L).
- Rate of hypoglycemia episodes, defined as number of episodes <70 mg/dL (3.9 mmol/L) for 15 min or more, as measured by CGM.
- Rate of clinically significant hypoglycemia episodes, defined as number of episodes <54 mg/dL (3.0 mmol/L) for 15 min or more, as measured by CGM.
- Extent of hypoglycemia (area over the glucose curve [AOC_{glucose}] below 70 mg/dL [3.9 mmol/L]) as measured by CGM.
- Extent of clinically significant hypoglycemia (AOC_{glucose} below 54 mg/dL [3.0 mmol/L]) as measured by CGM.
- CGM percent time in hyperglycemia (>180 mg/dL or 10.0 mmol/L).

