Adjustment of total carbohydrate administered (IV glucose, parenteral nutrition, carbohydrate infusions, and carbohydrates from oral feeds) should continue throughout this period according to local practice to maintain PG levels in the range of 70 mg/dL to 120 mg/dL (3.9-6.7 mmol/L). The aim will be to obtain stable glucose levels with minimum rescue/hypoglycemia-preventative carbohydrates administered by invasive routes, and to encourage/optimize oral feeds, and achieve weaning off IV glucose. Regardless of their discharge status, all patients will be offered the opportunity to participate in the long-term safety extension trial (ZP4207-17106), providing the investigator attests to the positive benefit-risk balance of continued dasiglucagon treatment.

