- **Weighted Mean IV GIR threshold:** This variable will be assigned “Yes” when the Weighted Mean IV GIR calculated over 12 hours period is not missing and < 10mg/kg/min and will be assigned “No” when value calculated will be $\geq 10\text{mg/kg/min}$.
- **Z-scores:** For subjects who are less than 2 years of age, WHO growth charts will be used to calculate Z-scores, as described here: 'www.cdc.gov/nccdphp/dnpao/growthcharts/resources/sas-who.htm'. For subjects who are greater than or equal to 2 years of age, Z-scores will be derived based on the SAS program in link 'www.cdc.gov/nccdphp/dnpao/growthcharts/resources/sas.htm' by using SEXN, Age in months ((VSDAT-ADSL.BRTHDT)/30.4375) and corresponding weight/height at baseline measurements.

- **PK Clearance:**

$$CL/f \text{ (L/h)} = R_0/C_{ss}$$

where R_0 = infusion rate (pmol/h) and C_{ss} = concentration at steady state (pmol/L), weight
($1\mu\text{g}/\text{kg}/\text{hr} = 295.7 \text{ nmol}/\text{kg}/\text{h}$)

- **Primary endpoint IV GIR:** Values from SDTM.EX where EXTRT="IV GLUCOSE INFUSION", not including the "IV GLUCOSE BOLUS".
- **Total amount of carbohydrates received:**

Calculated as the sum of carbohydrates received via IV glucose infusion or bolus, as part of total parenteral nutrition, via oral route and via NG tube or gastrostomy. This average daily value will be used in analysis calculated as the sum of carbohydrates received divided by number of days in corresponding period. As IV glucose infusion is recorded in mg/kg/min, for each analysis period, the total amount received will be calculated as:

$$\text{IV glucose infusion (mg)} = \text{Infusion rate recorded in CRF} \times \text{WGT} \times \text{TIME}$$

with WGT = weight at beginning of the analysis period, TIME = duration of analysis period in minutes

IV glucose infusion or bolus are reported in SDTM.EX with EXTRT in "IV GLUCOSE INFUSION" or "IV GLUCOSE BOLUS".

Carbohydrates received via oral route, via NG tube or gastrostomy are reported under Carbohydrates administration eCRF.

Total parenteral nutrition is reported under Carbohydrates administration eCRF selecting observations specified as part of TPN.

- **Nightly gastric carbohydrates to treat hypoglycemia** = amount of gastric carbohydrates (g) given between midnight and 6 am inclusive to treat hypoglycemia.

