8.3. Secondary Efficacy Analysis

The secondary efficacy analysis for this study includes the below summaries and inferential analyses. These are continuous endpoints and one binary endpoint and will be summarized using descriptive statistics by study visit (if applicable), treatment group (Part 1) and overall (Part 2) for patients in the FAS. Inference will be performed for Part 1 secondary endpoint as described below. For all the other endpoints no inference will be performed.

Missing data will be imputed for Weighted Mean IV GIR (continuous) as per what is described for primary analysis. The imputed Weighted Mean IV GIR will be used for derivation of Weighted Mean IV GIR below 10 mg/kg/min endpoint. No other imputation for missing data performed and no sensitivity analysis.

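### The home diary has no item for oral feeds, so the Part 2 total and oral-route carbohydrate endpoints have no described source for routine oral intake after discharge

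*Protocol*

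**What the plan says.** **Endpoint.** Protocol 7.2.3 lists for Part 2 "Total amount (g) of carbohydrates administered (regardless of the route) per day, together with amounts (g) of carbohydrates administered per day" by each of four routes, one of them oral. SAP 2.2.2 and 8.3.1 repeat this and present it by week and over the three weeks.

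**Derivation.** SAP 6.1.7 sums IV infusion or bolus and intake "as part of total parenteral nutrition, via oral route and via NG tube or gastrostomy". The daily value is "calculated as the sum of carbohydrates received divided by number of days in corresponding period". Oral and tube amounts are taken from the carbohydrate administration eCRF; the SAP does not say how that form is completed once the infant is at home.

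**Home record.** Protocol 11.2.1.3 introduces the diary list with "The following information should be recorded in the diary". Of six items, one concerns feeding: "Type and volume of fluid administered through NG tube/gastrostomy". The section adds "Data from the diary entries should be transcribed to the eCRF on an ongoing basis". The list is the same in version 14.0 (Germany) and version 13.0 (all other countries).

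**Missing data.** After the rules for the glucose infusion rate endpoints, SAP 8.3 states "No other imputation for missing data performed and no sensitivity analysis". SAP 8.3.1 sets carbohydrate to missing after pancreatectomy, and 8.3.2 repeats the Part 2 analyses without that rule. Neither deals with days at home.

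**Direction of care.** Protocol 10.2 gives as part of the Part 2 aim "to encourage/optimize oral feeds, and achieve weaning off IV glucose". Protocol 10.12 allows discharge once IV glucose has been weaned off and local criteria are met.

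**The concern.** The endpoint needs every route on every day, but the described home record covers only one of the routes by which an infant at home would be fed. The gap opens at discharge, which is itself a favourable event and follows IV weaning. It also widens with the oral share of feeding, which Protocol 6.3.7 names among the expected benefits.

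If blanks are added in as zero, the weekly total can fall because recording stops rather than because need falls, and the fall would look like benefit. The oral-route amount would drop in the infants who are feeding by mouth at home. Part 2 has no control arm against which such an artefact could be seen. If blanks are treated as missing, the weekly summaries come to describe mainly the infants still in hospital.

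**Working it through.** No figure in the plan is in dispute here, so there is none to reproduce. The check has two steps.

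**Step 1: is there another described home source of oral intake?**

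- Protocol 8.1 requires all feedings, including those by the normal route, to be recorded, but the sentence is about Part 1. There is no counterpart for Part 2.
- Protocol 11.2.3.3 collects type, amount and route of food, including oral, but only as the intervention for a hypoglycemic episode. Routine feeds are outside it.
- The Schedule of Events has diary recording after discharge and no separate feeding row.
- SAP 6.1.7 names the eCRF form but no home source for its oral field.

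No other source was found in either document.

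**Step 2: what does the SAP formula do with the gap?**

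Assumptions, none of them given in the documents: true total intake is constant, IV glucose has stopped by discharge, non-oral intake at home is recorded in the diary, and unrecorded oral intake adds 0. Let *s* be the oral share of intake at home and *k* the number of Part 2 days before discharge, out of 21.

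- Recorded total on a home day = true total × (1 − *s*), so the fall at discharge is *s*.
- Understatement of the 21-day mean = *s* × (21 − *k*) / 21. For *k* = 7 the factor is 14/21 = 0.667; for *k* = 14 it is 7/21 = 0.333.

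| Oral share at home | Fall in recorded total on a home day | 21-day mean understated, discharge after 7 days | 21-day mean understated, discharge after 14 days |
|---|---|---|---|
| 0% | 0% | 0% | 0% |
| 25% | 25% | 16.7% | 8.3% |
| 50% | 50% | 33.3% | 16.7% |
| 75% | 75% | 50.0% | 25.0% |
| 100% | 100% | 66.7% | 33.3% |

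On the same assumptions the recorded oral-route amount on a home day is about 0 whatever *s* is, apart from any oral food for a hypoglycemic episode that is carried across from that form.

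If a blank is instead treated as missing, no fall occurs. SAP 4.1 bases continuous summaries on non-missing values, so the affected home totals leave the weekly summaries.

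**The case against.** The strongest reply is that a protocol list is not a full inventory of what is collected. The Schedule of Events has no feeding row even for Part 1, where feedings are plainly recorded. The SAP names an eCRF form for oral carbohydrate, and the form, its completion guidelines and the printed diary are not among the documents. Sites may have completed the oral field from another source. That is possible, but for Part 1 the protocol states the requirement in its text, and for home days it does not. The least that is needed is to name the source.

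A reader might infer that every discharged infant will count as about 0 g/day and that the weekly totals are bound to fall. The documents do not support that:

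- The SAP does not say that a blank oral field becomes zero. Doing so would itself be an imputation, and SAP 8.3 rules out further imputation.
- Full oral feeding is not the stated aim of Part 2. Protocol 8.1 describes transfer to oral and gastric carbohydrates, and tube feeds at home are in the diary. A fully tube-fed infant loses nothing.
- It would be wrong to say that the SAP has no missing-data handling for this endpoint. The pancreatectomy rule applies to it, although that rule does not reach home days.

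The scope is also limited. Part 2 is single-arm and its endpoints are summarised without testing.

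**Conclusion.** The concern holds as a mismatch between data collection and endpoint. For infants fed partly or wholly by mouth at home, no described source captures routine oral intake, while the SAP divides the summed routes by all days in the period.

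The consequence depends on a rule that the SAP does not give. With blanks as zero, the recorded total falls at discharge by the oral share, anywhere from 0% to 100%, and the oral-route amount falls to about zero. With blanks as missing, the totals are lost and the remaining infants are a selected group. Neither result can be read as a change in carbohydrate need. The documents give no oral shares or discharge times, so only the range can be shown, and it rests on the assumptions listed with the calculation.

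Only the descriptive Part 2 total and oral-route carbohydrate endpoints are affected. The Part 1 primary and key secondary endpoints precede discharge and are untouched. The point should be fixed, but it does not threaten the trial's main conclusion.

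**What to change.** 1. **Diary, both protocol versions.** Add an item for the type and volume of oral feeds, with an explicit option for none, and transcribe it to the carbohydrate administration eCRF. If another home source already exists, name it in the protocol and SAP. The cost is one line and a little parent effort; volumes will be approximate for breast-fed infants. It helps only infants not yet discharged, and SAP 8.1 already refers to values in the database.

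2. **SAP 6.1.7 and 8.3.1.** State that unrecorded oral intake at home is not counted as zero. For total and oral-route carbohydrate, use days with complete route records as the denominator. Count a day as complete when exclusive tube feeding is documented, with oral intake a true zero. A rule that simply dropped home days with no oral entry would delete valid totals of tube-fed infants. Report the numbers of infants and days contributing each week, and show results by in-hospital or home status so that the selection is visible. Keep the IV and NG/gastrostomy endpoints on all days.

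The SAP change is wording and programming, and can be made before unblinded analysis. It follows the SAP's own practice for CGM, where percent time is divided by minutes of wear and extent of hypoglycemia by the duration of assessment.

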11.2.2. Pharmacokinetics/Drug Exposure

Blood samples will be collected in Part 2 to measure dasiglucagon levels at steady-state (Schedule of Events; Section 18.1). The blood samples should be collected after a minimum of 4 hours without changes to the dasiglucagon infusion rate. For patients with a body weight above 4 kg, an additional PK sample should be collected at Day 5. However, the total amount of blood collected should always be considered according to Section 11.2.3.1.

Details on sampling/collection, shipment, and analysis will be provided in the laboratory manual.

11.2.3. Safety

Safety assessments will include the evaluation of AEs, clinical laboratory assessments (hematology, biochemistry, and ADAs), vital signs, physical examinations, ECGs, echocardiography, and local tolerability.

11.2.3.1. Laboratory Safety Assessments

Trial procedures require a maximum total of 8.8 to 9.2 mL of blood in a 28-day period. Where this exceeds the 2.5 mL/kg maximum^{18,19}, safety laboratory tests (2 mL per sampling) will be prioritized over immunogenicity (1 mL) and drug exposure (0.4 mL) samples.

All measurements described in this section are recognized standard methods.

Hematology and Biochemistry

Samples for hematology and biochemistry will be collected at the time points specified in the Schedule of Events (Section 18.1).

Hematology: hemoglobin, hematocrit, red blood cell (RBC) count, RBC indices, mean corpuscular hemoglobin, mean corpuscular hemoglobin concentration, platelet count (or estimate), white blood cell count, including differential

Biochemistry: albumin, total bilirubin, total protein, calcium, alkaline phosphatase, alanine aminotransferase, aspartate aminotransferase, blood urea nitrogen, creatinine, glucose, sodium, potassium, chloride, eGFR, ketones (measured with PG meter)

Standard of care blood samples can be used as screening samples if they were collected within 1 week of screening.

Laboratory specimens will be analyzed at local laboratories.

Immunogenicity

Blood samples will be collected to test for antibodies against dasiglucagon at Visit 2 (Day 1, prior to dosing), Visit 7 (Day 25 ±3), and at the Follow-up Visit (Visit 8, Day 53 ±3) (Section 18.1) and processed and shipped according to instructions provided in the laboratory manual. The samples will be stored until the ADA screening and confirmatory assays have been approved by the FDA. Afterwards, the ADA samples will be analyzed in batches during the trial. The ADA samples will be analyzed at a specialty laboratory.

The clinical ADA assays specific for dasiglucagon and glucagon have been validated in accordance with existing guidelines and recommendations.^{19,21,22,23}

Samples will be measured in anti-dasiglucagon antibody screening and confirmatory assays. Due to the limited sample volume, the ADA characterization of confirmed positive samples will be conducted according to the following priority:

- Establishment of anti-dasiglucagon binding titer.
- Cross-reactivity against endogenous glucagon

The neutralizing potential in samples from ADA-positive patients will be evaluated on the basis of drug exposure/PD data (steady-state exposure and PG).

The ADA samples will be analyzed in batches during the trial and any anti-dasiglucagon antibody-positive patients (treatment induced or treatment boosted, titer increase above 5-fold)

will be monitored at an additional follow-up visit, preferably 16 weeks after last ADA-positive sample. Patients who complete the trial before the ADA screening and confirmatory assays have been approved by the FDA and who do not continue treatment in the long-term extension trial will have this additional visit 16 weeks after the end of trial visit (Visit 8). Patients who are tested ADA positive after the additional Follow-up Period will be categorized as having persistent antibodies.

It will not be possible to collect back-up ADA samples for long-term storage due to limited blood volume in these patients. However, any residual serum samples may be stored until approval of market authorization since further characterization of the antibody response may be requested.

Specimen Handling Requirements

The transmission of infectious agents may occur through contact with contaminated needles and blood or blood products. Consequently, appropriate blood and body fluid precautions should be employed by all trial personnel involved in the collection of blood and handling of specimens in both the clinic and laboratory settings. Refer to current recommendations of the appropriate authorities.

In addition to appropriate handling of patient samples, specific regulations exist regarding the shipment of biologic/etiological samples. Procedures and regulations for the packaging and shipping of infectious samples are outlined in the laboratory manual. The investigator is responsible for ensuring that all trial samples that are to be transported to another location are packed and shipped appropriately according to the applicable regulations.

Evaluation of Laboratory Values

The normal ranges of values for the laboratory assessments in this trial will be provided by the responsible laboratories and submitted to the sponsor before the beginning of the trial. They will be regarded as the reference ranges on which decisions will be made.

If a laboratory value is out of the reference range, the investigator must evaluate if the value is clinically significant and record his or her assessment in the appropriate eCRF.

All laboratory values that in the investigator's opinion are clinically relevant during or after termination of the treatment have to be reported as AEs and followed, as described in Section 12.3.

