10.2. Treatments Administered

As long as the patient is receiving IV glucose, the PG will be measured and reviewed hourly using a hand-held PG meter. The IV GIR will be titrated to achieve glycemia of at least 70 mg/dL (3.9 mmol/L) (a minimum GIR will be established as the rate up-titrated after the patient drops at least once below 70 mg/dL [3.9 mmol/L]). When the patient is no longer on IV GIR, the PG will be checked according to local practice, but at least 3 times daily. The PG will be measured using the same trial-supplied hand-held PG meter during the entire trial.

Additionally, blinded CGM will be started 24 hours prior to randomization and continued until the end of Part 2.

Dosing of dasiglucagon will approximate continuous infusion by delivering small doses at frequent intervals via the infusion pump. The adjustment of trial drug dosing is closely linked to the PG level achieved, which in turn will govern the IV GIR. In Part 1 the algorithm in [Table 1](#) should be used.

The pump administers 0.000025 mL/dose ~ 0.1 µg/dose (4 mg/mL formulation):

- 10 µg/hr ~ 0.5 µg every 3 min
- 20 µg/hr ~ 1 µg every 3 min
- 30 µg/hr ~ 1.5 µg every 3 min
- 40 µg/hr ~ 2 µg every 3 min
- 50 µg/hr ~ 2.5 µg every 3 min
- 60 µg/hr ~ 3 µg every 3 min
- 70 µg/hr ~ 3.5 µg every 3 min

Table 1 Algorithm to Maintain Plasma Glucose

Plasma Glucose (mg/dL)	Plasma Glucose (mmol/L)	Action
<50	<2.8	Give 200 mg/kg of dextrose as a bolus and increase IV GIR by 2 mg/kg/min
50-59	2.8-3.3	Increase IV GIR by 2 mg/kg/min
60-69	3.3-3.9	Increase IV GIR by 1 mg/kg/min
70-80	3.9-4.4	No change
81-90	4.4-5.0	Reduce IV GIR by 0.5 mg/kg/min
91-100	5.0-5.5	Reduce IV GIR by 1 mg/kg/min
101-120	5.5-6.7	Reduce IV GIR by 1.5 mg/kg/min
>120	>6.7	Reduce IV GIR by 2 mg/kg/min

Abbreviations: GIR = glucose infusion rate; IV = intravenous

The IV GIR will be reviewed, evaluated, and adjusted (if indicated) every hour according to the above PG-driven algorithm to maintain a PG of >70 mg/dL (>3.9 mmol/L). Rechecks of PG are allowed.

Part 1 (Crossover, double-blind, randomized, placebo-controlled)

The starting dose of trial drug is 10 µg/hr at t=0. Every 2 hours (t=2, 4, 6, etc.), the dose will be increased by an additional 10 µg/hr until either:

- The patient is totally weaned off IV glucose, or
- Plasma glucose during the last 2 hours was constantly above 120 mg/dL (6.7 mmol/L), or

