- IV GIR has not decreased despite 2 sequential dose increments of trial drug (in this situation, the dose of trial drug should be maintained until the IV GIR can be further decreased or until crossover or the end of Part 1), or
- The maximum dose of 70 µg/hr is reached, or
- AEs emerge that are considered to be related to dasiglucagon (e.g., nausea/change in feeding pattern or increased vomiting) that are limiting further dose escalation

The 2-hour dose-adjustment interval will allow drug plasma levels to approach steady-state before the dose is further increased. The cumulative dose will not exceed 1.26 mg over the first 24 hours and 1.68 mg for each of the subsequent 24-hour periods.

At the time of crossover from the first 48-hour period to the second 48-hour period, the trial drug will again be titrated from the starting dose of 10 µg/hr, and IV GIR will be set to the rate obtained at the end of the run-in period and titrated accordingly.

Part 2 (Open label)

After Part 1, patients will continue in open-label Part 2 to receive dasiglucagon for a further 21 days. Since treatment allocation during Part 1 remains blinded, all patients are required to initiate dasiglucagon dosing at 10 µg/hr in Part 2, while IV GIR should be started at the rate obtained at the end of the run-in period.

During Part 2, the dasiglucagon dose, the amount and route of administration of carbohydrates (IV GIR, parenteral nutrition, gastric carbohydrate infusions, and carbohydrates from oral feeds) can be adjusted at the discretion of the investigator. The PG should be monitored at least hourly to adjust the IV GIR as appropriate and to avoid hypoglycemia. Additional concomitant medications, including somatostatin analogs and/or sirolimus/mTOR inhibitors, may be introduced at the investigator's discretion if the maximum dose level of dasiglucagon (70 µg/hr) has been reached or if further up-titration is not possible due to undesirable side effects.

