11.2.3.1. Laboratory Safety Assessments

Trial procedures require a maximum total of 8.8 to 9.2 mL of blood in a 28-day period. Where this exceeds the 2.5 mL/kg maximum,^{18,19} safety laboratory tests (2 mL per sampling) will be prioritized over immunogenicity (1 mL) and drug exposure (0.4 mL) samples.

All measurements described in this section are recognized standard methods.

Hematology and Biochemistry

Samples for hematology and biochemistry will be collected at the time points specified in the Schedule of Events (Section 18.1).

Hematology: hemoglobin, hematocrit, red blood cell (RBC) count, RBC indices, mean corpuscular hemoglobin, mean corpuscular hemoglobin concentration, platelet count (or estimate), white blood cell count, including differential

Biochemistry: albumin, total bilirubin, total protein, calcium, alkaline phosphatase, alanine aminotransferase, aspartate aminotransferase, blood urea nitrogen, creatinine, glucose, sodium, potassium, chloride, eGFR, ketones (measured with PG meter)

Standard of care blood samples can be used as screening samples if they were collected within 1 week of screening.

Laboratory specimens will be analyzed at local laboratories.

Immunogenicity

Blood samples will be collected to test for antibodies against dasiglucagon at Visit 2 (Day 1, prior to dosing), Visit 7 (Day 25 ±3), and at the Follow-up Visit (Visit 8, Day 53 ±3) (Section 18.1) and processed and shipped according to instructions provided in the laboratory manual.

The samples will be stored until the ADA screening and confirmatory assays have been approved by the FDA. Afterwards, the ADA samples will be analyzed in batches during the trial. The ADA samples will be analyzed at a specialty laboratory.

The clinical ADA assays specific for dasiglucagon and glucagon have been validated in accordance with existing guidelines and recommendations.^{19,21,22,23}

Samples will be measured in anti-dasiglucagon antibody screening and confirmatory assays. Due to the limited sample volume, the ADA characterization of confirmed positive samples will be conducted according to the following priority:

- Establishment of anti-dasiglucagon binding titer.
- Cross-reactivity against endogenous glucagon.

The neutralizing potential in samples from ADA-positive patients will be evaluated on the basis of drug exposure/PD data (steady-state exposure and PG).

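### Neutralizing potential of anti-drug antibodies is to be judged from drug exposure and plasma glucose only, but Part 2 titration holds plasma glucose near target and would largely mask a gradual loss of drug effect

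*Protocol*

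**What the plan says.** **Antibody assessment.** Protocol 11.2.3.1, with the same wording in versions 13.0 and 14.0, says: "The neutralizing potential in samples from ADA-positive patients will be evaluated on the basis of drug exposure/PD data (steady-state exposure and PG". On laboratory work-up it says: "Due to the limited sample volume, the ADA characterization of confirmed positive samples will be conducted according to the following priority". Two items follow, binding titer and cross-reactivity with endogenous glucagon. No neutralizing assay is listed.

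**Sampling.** Antibodies are sampled on Day 1 before dosing, on Day 25, and on Day 53 in patients who do not enter the extension trial. Exposure is sampled on Day 6 and Day 25, with an extra Day 5 sample in heavier infants (Schedule of Events; SAP 2.2.3).

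**Titration.** Protocol 10.2 says: "The adjustment of trial drug dosing is closely linked to the PG level achieved, which in turn will govern the IV GIR". In Part 2 the dose and the amount and route of carbohydrates "can be adjusted at the discretion of the investigator. The PG should be monitored at least hourly to adjust the IV GIR as appropriate". Carbohydrate is further adjusted "according to local practice to maintain PG levels in the range of 70 mg/dL to 120 mg/dL". Somatostatin analogs, diazoxide and other CHI drugs may be added under conditions (Protocol 10.2 and 10.11.1).

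**SAP.** Section 9.2 covers antibody incidence and titers descriptively and does not mention neutralization. Infusion rate (7.4), carbohydrate by route (8.3.1) and concentrations by infusion rate (11.1) are summarized, but none of them by antibody status.

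**The concern.** A pharmacodynamic marker of neutralization should move when the drug stops working. In Part 2, PG is what the clinical team steers. If drug effect fades, the expected response is a higher dasiglucagon rate, a rise or restart of IV GIR, more carbohydrate, or an added CHI drug, with PG brought back towards target. The sentence in 11.2.3.1 names none of these.

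The trial applies the sounder logic to efficacy: its primary endpoint is IV GIR and its key secondary endpoint is total carbohydrate (Protocol 7.2.1 and 7.2.2).

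At stake is the immunogenicity conclusion. A patient whose antibodies weaken the drug could be reported without evidence of neutralization because PG looks unchanged.

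**Working it through.** The plan gives no figure on this point, so the check is a comparison of passages, one size calculation and an illustration.

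**1. What each quantity does under gradual loss of effect**

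| Quantity | Role in Part 2 | Expected change | Named in 11.2.3.1 for neutralization? |
|---|---|---|---|
| PG | Steered to target | Small | Yes |
| Steady-state concentration | Measured Day 6, Day 25 | Only if antibodies alter drug levels | Yes |
| Dasiglucagon rate | Adjustable | Up | No |
| IV GIR | Adjustable | Up or restarted | No |
| Other carbohydrate | Adjustable | Up | No |
| Added CHI drugs | Permitted under conditions | More use | No |

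**2. Size of the signal.** Inputs: assumed effect 7.5 mg/kg/min (Protocol 13.2) and the 3 kg infant used for the exposure estimate (Protocol 10.7).

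7.5 mg/kg/min × 3 kg × 1,440 min/day = 32,400 mg/day = 32.4 g/day of extra glucose to hold the same PG after complete loss.

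**3. Speed of loss against speed of titration.** Assume the effect fades over 14 days: 7.5 / 14 = 0.54 mg/kg/min per day. Table 1 of Protocol 10.2 raises GIR by 1 or 2 mg/kg/min at a single hourly review when PG is below 70 mg/dL, so titration easily keeps up. If all 7.5 mg/kg/min were lost at once, replacement would take 7.5 / 2 = 3.75 to 7.5 / 1 = 7.5 hours, that is, about 4 to 8 hourly steps with PG low. Abrupt loss could therefore be seen in PG.

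**4. Illustration by simulation.** Assumptions not taken from the documents: total glucose need 15 mg/kg/min; drug effect 7.5 mg/kg/min at the start, then kept, halved or lost over 14 days; PG response of 2, 5 or 10 mg/dL per mg/kg/min per hour; PG otherwise moving halfway back to 75 mg/dL each hour; noise SD 6 mg/dL; drug dose fixed. GIR follows the Table 1 steps hourly, without the dextrose bolus. Table 1 is the Part 1 algorithm, used here in place of Part 2 practice. Results are means over the last 72 hours, with ranges across the three PG responses.

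| Drug effect | Titrated: PG (mg/dL) | Titrated: GIR (mg/kg/min) | Titrated: readings <70 mg/dL | GIR fixed, response 2: PG (mg/dL) |
|---|---|---|---|---|
| Kept | 76.8–77.2 | 7.6–8.0 | 17.0–20.2% | 75.0 |
| Halved | 76.9–77.2 | 11.4–11.7 | 17.1–20.4% | 60.0 |
| Lost | 76.9–77.3 | 15.1–15.4 | 17.5–20.3% | 44.8 |

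The GIR column agrees with the simple balance, need minus effect: 15 − 7.5 = 7.5; 15 − 3.75 = 11.25; 15 − 0 = 15. Under titration the loss moves into GIR; it lowers PG only when GIR is fixed.

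**5. The exposure marker.** SAP 6.1.7 defines CL/f = R0/Css (infusion rate over steady-state concentration). A change from Day 6 to Day 25 would show that antibodies alter drug levels. If they block activity and leave the measured concentration unchanged, CL/f does not move.

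**6. Day 53.** This visit falls 28 days after Day 25. Treatment has ended and no exposure sample is scheduled, so neither marker can inform on neutralization then.

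**The case against.** Several arguments on the other side are sound and limit the point.

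- **PG is not blind to drug effect.** In the 40-infant review cited in Protocol 6.3.4, starting glucagon lowered GIR from 18.5 to 11 mg/kg/min and hypoglycemia from 1.9 to 0.7 episodes per day. Hypoglycemia by meter and by continuous monitoring (CGM) is also a Part 2 endpoint. After discharge, PG is checked at least 3 times daily, which is not tight control. A reader might infer that loss of effect could never appear in PG; the documents do not support that. Largely masked, for gradual loss during active titration, is as far as the argument goes.
- **No decision rule is written.** The protocol names data sources and gives no threshold. A reader might infer that unchanged PG automatically classes a patient as non-neutralizing; it does not. But the SAP supplies no criterion either, so the omission stands.
- **Rollover.** A reader might infer that harm arises before entry to the extension. Samples are batched, entry rests on the investigator's benefit-risk judgement (Protocol 10.13), and extra antibody follow-up depends on treatment-induced or boosted positivity, not on neutralization.
- **Blood volume.** A reader might infer that exposure samples are the first to be dropped in small infants. The text says "safety laboratory tests (2 mL per sampling) will be prioritized over immunogenicity (1 mL) and drug exposure (0.4 mL) samples". It puts both below safety tests and does not rank one against the other.
- **Partly planned already.** CL/f, weekly infusion rate and weekly carbohydrate by route are in the SAP, and residual serum may be kept for further characterization. What is missing is the link to antibody status.
- **The added variables have limits.** Planned transfer from IV glucose to feeds and changing needs confound trends, and one on-treatment post-baseline sample does not date antibody onset. These are reasons for cautious reading, not for leaving the variables out.
- **Few cases are expected.** The trial plans 12 patients, and Protocol 6.3.6 reports one low-titer transient case among more than 200 patients in other indications.

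**Conclusion.** The point holds in a limited form. Exposure and PG alone are a weak basis for judging neutralization, because Part 2 care steers PG and concentration does not show activity. The consequence is a risk of a false-negative immunogenicity conclusion in any antibody-positive patient. No hypothesis, efficacy endpoint or treatment decision depends on it.

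The 32.4 g/day figure assumes the full 7.5 mg/kg/min effect, a 3 kg infant and complete loss; it scales in proportion to each. The simulation shows direction only, under its stated assumptions and with the Part 1 algorithm in place of investigator discretion. In a child already weaned off IV glucose, the signal would be sought in dose, enteral carbohydrate, added drugs, a restart of IV glucose, or hypoglycemia. With few positive patients expected, one misreading could change the trial's summary, and the correction is cheap, so it should be made.

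**What to change.** **Protocol 11.2.3.1, both versions.** Replace the bracketed pair of markers with: steady-state exposure, including CL/f, read together with dasiglucagon infusion rate (µg/kg/hr), IV GIR, recorded carbohydrate per kg per day, added CHI drugs, and PG and CGM hypoglycemia, before and at the antibody-positive sample. State that a Day 53 sample cannot be judged in this way.

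**SAP 9.2.** Add one per-patient listing or plot of these variables over Part 2 for each patient with treatment-induced or treatment-boosted antibodies. Note on it that the home diary (Protocol 11.2.1.3) lists tube and gastrostomy fluids but not oral feeds, so carbohydrate after discharge may be incomplete.

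**Cost.** A wording change and one display built from data already recorded. It requires no new samples and no change to dosing or clinical management.
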